11.2 Database management and quality control

Novartis personnel (or designated CRO) will review the data entered by investigational staff for completeness and accuracy. Electronic data queries stating the nature of the problem and requesting clarification will be created for discrepancies and missing values and sent to the investigational site via the EDC system. Designated investigator site staff are required to respond promptly to queries and to make any necessary changes to the data.

Concomitant treatments and prior medications entered into the database will be coded using the WHO Drug Reference List, which employs the Anatomical Therapeutic Chemical classification system. Medical history/current medical conditions and adverse events will be coded using the Medical dictionary for regulatory activities (MedDRA) terminology.

At the conclusion of the study, the occurrence of any emergency code breaks will be determined after return of all code break reports and unused supplies to Novartis.

Once all the necessary actions have been completed and the database has been declared to be complete and accurate, it will be locked **and the treatment codes will be unblinded** and made available for data analysis/moved to restricted area to be accessed by independent programmer and statistician. Any changes to the database after that time can only be made after written agreement by Novartis development management.

Commercially Confidential Information

11.3 Site monitoring

Before study initiation, at a site initiation visit or at an investigator's meeting, a Novartis or delegated CRO representative will review the protocol and data capture requirements (i.e. eSource or eCRFs) with the investigators and their staff. During the study, Novartis employs several methods of ensuring protocol and GCP compliance and the quality/integrity of the sites' data. The field monitor will visit the site to check the completeness of subject records, the accuracy of data capture / data entry, the adherence to the protocol and to Good Clinical Practice, the progress of enrollment, and to ensure that study treatment is being stored, dispensed, and accounted for according to specifications. Key study personnel must be available to assist the field monitor during these visits. Continuous remote monitoring of each site's data may be performed by a centralized Novartis/delegated CRO/CRA organization. Additionally, a central analytics organization may analyze data & identify risks & trends for site operational parameters, and provide reports to Novartis clinical teams to assist with trial oversight.

The investigator must maintain source documents for each subject in the study, consisting of case and visit notes (hospital or clinic medical records) containing demographic and medical information, laboratory data, electrocardiograms, and the results of any other tests or assessments. All information on CRFs must be traceable to these source documents in the subject's file. The investigator must also keep the original informed consent form signed by the subject (a signed copy is given to the subject).

The investigator must give the monitor access to all relevant source documents to confirm their consistency with the data capture and/or data entry. Novartis monitoring standards require full verification for the presence of informed consent, adherence to the inclusion/exclusion criteria, documentation of SAEs, and of data that will be used for all primary variables. Additional checks of the consistency of the source data with the CRFs are performed according to the study-specific monitoring plan. No information in source documents about the identity of the subjects will be disclosed.

12 Data analysis and statistical methods

The analysis will be conducted on all subject data at the time the trial ends, under the direction of Novartis personnel in compliance with internal documents and standards.

12.1 Analysis sets

For all analysis sets, subjects will be analyzed according to the study treatment received, where treatment received is defined as the randomized/assigned treatment if the patient took at least one dose of that treatment or the first treatment received if the randomized/assigned treatment was never received.

The safety analysis set includes all subjects who received at least one dose of any study treatment.

The PK analysis set will include all subjects with at least one valid (i.e. not flagged for exclusion) KAE609 concentration data, who received study drug and had no protocol deviations with relevant impact on the interpretability of the PK data.

Within a study part, all placebo subjects from all cohorts will be pooled.

12.2 Subject demographics and other baseline characteristics

Demographic and other baseline data will be listed by part, treatment group and subject. Summary statistics will be provided by part and treatment group for the safety set.

Categorical data will be presented as frequencies and percentages. For continuous data, mean, standard deviation, median, minimum, and maximum will be presented.

Relevant medical histories and current medical conditions at baseline will be listed by part, treatment group and subject.

12.3 Treatments

The safety set will be used for the analyses below.

Data for study treatment administration, concomitant medications and significant non-drug therapies prior to and after the start of the study treatment will be listed by part, treatment group and subject.

12.4 Analysis of the primary endpoint(s)

The primary aim of the study is to determine the safety and tolerability of KAE609 after single and multiple iv doses in healthy subjects. All safety analyses will be performed on the safety analysis set.

12.4.1 Definition of primary endpoint(s)

The primary endpoints are safety and tolerability assessments including adverse events, vital signs, ECG findings (including QTcF), safety laboratory assessments including chemistry, hematology, and urinalysis results assessed at baseline up to Day 8 in Part A and up to Day 12 in Part B (EOS).

12.4.2 Statistical model, hypothesis, and method of analysis

For all safety analyses, the safety set will be used. All listings and tables will be presented by treatment group. Graphical representations of the safety data may be produced.

Adverse events

All information obtained on adverse events will be displayed by part, treatment group and subject. The number and percent of patients with adverse events will be tabulated by system organ class and preferred term with a breakdown by treatment group. A subject with multiple adverse events within a system organ class is only counted once towards the total of the system organ class. Separate tables and listings will present adverse event severity (CTCAE grade) and relationship to study treatment.

The number (and percent) of subjects with adverse events of infusion site reaction may be summarized by treatment group.

Vital signs

If normal ranges are available, vital signs abnormalities (and relevant orthostatic changes) will be flagged and will be listed by part, subject and visit/time. Summary statistics may be provided by part, treatment group and visit/time.

ECG evaluations

Abnormal ECG data will be flagged and will be listed by part, treatment group, subject and visit/time. Summary statistics may be provided by part, treatment group and visit/time.

Holter ECG data analysis

The relationship between change from baseline in time-matched QTcF and KAE609 plasma concentration will be explored using linear mixed effects modeling. Other ECG parameters (QT, QTcB, HR, PR interval and QRS) will be summarized. Data from the SAD and MAD parts of the study will be pooled for this assessment. The change from baseline in QTcF will be the dependent variable in the model, KAE609 plasma concentration will be a covariate, and time a categorical variable. A random intercept for each subject will be specified. Placebo subjects will be included in the analysis with a plasma concentration of 0. The placebo-corrected change from baseline in QTcF and the two-sided 90% confidence interval will be extracted from the model at the geometric mean maximum plasma concentration for each treatment.

A plot of raw QTcF change vs KAE609 plasma concentration will be presented together with the estimated slope and 90% Confidence Interval (CI) from the statistical model.

The analysis results for categorical outliers and T-wave morphology will be summarized in frequency tables with counts and percentages for both number of subjects and number of timepoints. For categorical outliers, the number of subjects (%) and timepoints will be determined by treatment group for the following:

- increase in QTcF from baseline of > 30 msec and > 60 msec
- absolute QTcF values > 500 msec
- PR change from baseline > 25% increase resulting in PR > 220 msec
- QRS change from baseline > 25% increase resulting in QRS > 120 msec
- heart rate change from baseline > 25% decrease resulting in heart rate < 50 beats per minute
- heart rate change from baseline > 25% increase resulting in a heart rate > 100 beats per minute

For T-wave morphology, the analysis will be focused on the treatment emergent changes.

Clinical laboratory evaluations

If normal ranges are available, laboratory data abnormalities will be flagged and will be listed by part, treatment group, subject and visit/time. Summary statistics may be provided by part, treatment group and visit/time.

Individual profile plots of laboratory data (e.g. sodium, potassium, calcium, AST and ALT) will be provided. Graphical summary of these laboratory parameters will also be provided by part and treatment group.

12.4.3 Handling of missing values/censoring/discontinuations

No imputation of missing data will be considered for safety and tolerability analysis.

12.4.4 Sensitivity and Supportive analyses

Not applicable.

12.5 Analysis of secondary endpoints

The secondary objective is to evaluate the pharmacokinetics of single and multiple ascending iv doses of KAE609 in healthy subjects.

12.5.1 Pharmacokinetics

For each part, KAE609 plasma concentration data will be listed by subject, and visit/sampling time point. Descriptive summary statistics will be provided by treatment and visit/sampling time point, Commercially Confidential Information

Summary statistics will include mean (arithmetic and geometric), SD, CV (arithmetic and geometric), median, minimum and maximum. Commercially Confidential Information

PK parameters will be listed by subject. Descriptive summary statistics will include mean (arithmetic and geometric), SD, and CV (arithmetic and geometric), median, minimum and maximum. An exception to this is Tmax where median, minimum and maximum will be presented.

Commercially Confidential Information

PK concentration data from this study may be used for population PK modeling. If performed, the results will be reported separately.

Table 12-1 Non-compartmental pharmacokinetic parameters

AUC0-t	The AUC from time zero to time t (e.g. 24h) (mass x time x volume-1)
AUClast	The AUC from time zero to the last measurable concentration sampling time (tlast) (mass x time x volume-1)
AUCinf	The AUC from time zero to infinity (mass x time x volume-1)
AUCtau	The AUC calculated to the end of a dosing interval (tau) at steady-state (amount x time x volume-1)
Cmax	The maximum (peak) observed plasma, blood, serum, or other body fluid drug concentration after single dose administration (mass x volume-1)
Tmax	The time to reach maximum (peak) plasma, blood, serum, or other body fluid drug concentration after single dose administration (time)
T1/2	The elimination half-life associated with the terminal slope (lz) of a semi logarithmic concentration-time curve (time). Use qualifier for other half-lives
CL	The total body clearance of drug from the plasma (volume x time-1)
Vss	The apparent volume of distribution at steady state from an intravenously administered dose (volume)

12.6 Analysis of exploratory endpoints

Commercially Confidential Information

Commercially Confidential Information

12.7 Interim analyses

Commercially Confidential Information

12.8 Sample size calculation

12.8.1 Primary endpoint(s)

In Part A, 8 subjects will be enrolled into each dose level cohort. Six of the subjects in each cohort will receive KAE609 and 2 subjects will receive placebo. In Part B, 9 subjects will be enrolled in each dose level cohort with 6 subjects receiving KAE609 and 3 subjects receiving placebo.

With 6 subjects receiving KAE609 in each iv cohort in Part A and Part B, it is highly probable that adverse events will be observed if the underlying adverse event rate is medium to high. For instance, if the underlying adverse event rate is 1 in every 5 subjects then there is a 74% chance that this adverse event will be detected in at least 1 subject on active treatment. Conversely, adverse events with low event rates are unlikely to be detected in this part of the study. For instance, if the underlying adverse event rate is 1 in every 100 subjects then the probability of observing this adverse event in at least 1 subject on active treatment is only 6%.

Table 12-2 Probability of observing events given a range of underlying event rates in Part A and Part B

Underlying event rate	Probability of observing no subjects* with adverse event	Probability of observing at least 1 subject* with adverse event	Probability of observing at least 2 subjects* with adverse event
1 in 100	94%	6%	< 1%
1 in 20	74%	26%	3%
1 in 10	53%	47%	11%
1 in 5	26%	74%	34%
1 in 2	2%	98%	89%

* Out of 6 subjects on active treatment

13 Ethical considerations and administrative procedures

13.1 Regulatory and ethical compliance

This clinical study was designed and shall be implemented, executed and reported in accordance with the ICH Harmonized Tripartite Guidelines for Good Clinical Practice, with applicable local regulations (including European Directive 2001/20/EC, US CFR 21), and with the ethical principles laid down in the Declaration of Helsinki.

13.2 Responsibilities of the investigator and IRB/IEC

Before initiating a trial, the investigator/institution must obtain approval/favorable opinion from the Institutional Review Board/Independent Ethics Committee (IRB/IEC) for the trial protocol, written informed consent form, consent form updates, subject recruitment procedures (e.g., advertisements) and any other written information to be provided to subjects. Prior to study start, the investigator is required to sign a protocol signature page confirming his/her agreement to conduct the study in accordance with these documents and all of the instructions and procedures found in this protocol and to give access to all relevant data and records to Novartis monitors, auditors, Novartis Quality Assurance representatives, designated agents of Novartis, IRBs/IECs, and regulatory authorities as required. If an inspection of the clinical site is requested by a regulatory authority, the investigator must inform Novartis immediately that this request has been made.

13.3 Publication of study protocol and results

This study only involves healthy subjects and as such Novartis will register the protocol as required to databases specified by local regulations (e.g. EudraCT during CTA filing for studies in EU/EEA). After study completion (defined as last patient last EOS visit) and finalization of the study report, results of this trial may be submitted for publication (e.g. peer-reviewed journal) or registered to databases where required by local regulations.

For details on the Novartis publication policy including authorship criteria, please refer to the Novartis publication policy training materials that were provided to you at the site initiation visit.

13.4 Quality Control and Quality Assurance

Novartis maintains a robust Quality Management System (QMS) that includes all activities involved in quality assurance and quality control, to ensure compliance with written Standard Operating Procedures as well as applicable global/local GCP regulations and ICH Guidelines.

Audits of investigator sites, vendors, and Novartis systems are performed by auditors, independent from those involved in conducting, monitoring or performing quality control of the clinical trial. The clinical audit process uses a knowledge/risk based approach.

Audits are conducted to assess GCP compliance with global and local regulatory requirements, protocols and internal SOPs, and are performed according to written Novartis processes

14 Protocol adherence

This protocol defines the study objectives, the study procedures and the data to be collected on study participants. Additional assessments required to ensure safety of subjects should be administered as deemed necessary on a case by case basis. Under no circumstances including incidental collection is an investigator allowed to collect additional data or conduct any additional procedures for any purpose involving any investigational drugs under the protocol, other than the purpose of the study. If despite this interdiction prohibition, data, information, observation would be incidentally collected, the investigator shall immediately disclose it to Novartis and not use it for any purpose other than the study, except for the appropriate monitoring on study participants.

Investigators ascertain they will apply due diligence to avoid protocol deviations. If an investigator feels a protocol deviation would improve the conduct of the study this must be considered a protocol amendment, and unless such an amendment is agreed upon by Novartis and approved by the IRB/IEC and health authorities, where required, it cannot be implemented.

16.1 Appendix 1: Liver event and Laboratory trigger Definitions and Follow-up Requirements

Table 16-1 Liver Event and Laboratory Trigger Definitions

	Definition/ threshold
LIVER LABORATORY TRIGGERS	
 • $3 \times \text{ULN} < \text{ALT} / \text{AST} \leq 5 \times \text{ULN}$ • $1.5 \times \text{ULN} < \text{TBL} \leq 2 \times \text{ULN}$
LIVER EVENTS	
 • $\text{ALT or AST} > 5 \times \text{ULN}$ • $\text{ALP} > 2 \times \text{ULN}$ (in the absence of known bone pathology) • $\text{TBL} > 2 \times \text{ULN}$ (in the absence of known Gilbert syndrome) • $\text{ALT or AST} > 3 \times \text{ULN}$ and $\text{INR} > 1.5$ • Potential Hy's Law cases (defined as $\text{ALT or AST} > 3 \times \text{ULN}$ and $\text{TBL} > 2 \times \text{ULN}$ [mainly conjugated fraction] without notable increase in ALP to $> 2 \times \text{ULN}$) • Any clinical event of jaundice (or equivalent term) • $\text{ALT or AST} > 3 \times \text{ULN}$ accompanied by (general) malaise, fatigue, abdominal pain, nausea, or vomiting, or rash with eosinophilia • Any adverse event potentially indicative of a liver toxicity*

*These events cover the following: hepatic failure, fibrosis and cirrhosis, and other liver damage-related conditions; the non-infectious hepatitis; the benign, malignant and unspecified liver neoplasms TBL: total bilirubin; ULN: upper limit of normal

Table 16-2 Follow Up Requirements for Liver Events and Laboratory Triggers

Criteria	Actions required	Follow-up monitoring
Potential Hy's Law case ^a	
 • Discontinue the study treatment immediately • Hospitalize, if clinically appropriate • Establish causality • Complete liver CRF 	ALT, AST, TBL, Alb, PT/INR, ALP and γ GT until resolution ^c (frequency at investigator discretion)
ALT or AST > $8 \times \text{ULN}$	
 • Discontinue the study treatment immediately • Hospitalize if clinically appropriate • Establish causality • Complete liver CRF 	ALT, AST, TBL, Alb, PT/INR, ALP and γ GT until resolution ^c (frequency at investigator discretion)

Criteria	Actions required	Follow-up monitoring
> 3 × ULN and INR > 1.5	
 Discontinue the study treatment immediately Hospitalize, if clinically appropriate Establish causality Complete liver CRF 	ALT, AST, TBL, Alb, PT/INR, ALP and γGT until resolution ^c (frequency at investigator discretion)
> 5 to ≤ 8 × ULN	
 Repeat LFT within 48 hours If elevation persists, continue follow-up monitoring If elevation persists for more than 2 weeks, discontinue the study drug Establish causality Complete liver CRF 	ALT, AST, TBL, Alb, PT/INR, ALP and γGT until resolution ^c (frequency at investigator discretion)
> 3 × ULN accompanied by symptoms ^b	
 Discontinue the study treatment immediately Hospitalize if clinically appropriate Establish causality Complete liver CRF 	ALT, AST, TBL, Alb, PT/INR, ALP and γGT until resolution ^c (frequency at investigator discretion)
> 3 to ≤ 5 × ULN (patient is asymptomatic)	
 Repeat LFT within the next week If elevation is confirmed, initiate close observation of the patient 	Investigator discretion Monitor LFT within 1 to 4 weeks
ALP (isolated)		
> 2 × ULN (in the absence of known bone pathology)	
 Repeat LFT within 48 hours If elevation persists, establish causality Complete liver CRF 	Investigator discretion Monitor LFT within 1 to 4 weeks or at next visit
TBL (isolated)		
> 2 × ULN (in the absence of known Gilbert syndrome)	
 Repeat LFT within 48 hours If elevation persists, discontinue the study drug immediately Hospitalize if clinically appropriate Establish causality Complete liver CRF 	ALT, AST, TBL, Alb, PT/INR, ALP and γGT until resolution ^c (frequency at investigator discretion) Test for hemolysis (e.g., reticulocytes, haptoglobin, unconjugated [indirect] bilirubin)

Criteria	Actions required	Follow-up monitoring
> 1.5 to $\leq 2 \times$ ULN (patient is asymptomatic)	
 Repeat LFT within the next week If elevation is confirmed, initiate close observation of the patient 	Investigator discretion Monitor LFT within 1 to 4 weeks or at next visit
Jaundice	
 Discontinue the study treatment immediately Hospitalize the patient Establish causality Complete liver CRF 	ALT, AST, TBL, Alb, PT/INR, ALP and γ GT until resolution ^c (frequency at investigator discretion)
Any AE potentially indicative of a liver toxicity*	
 Consider study treatment interruption or discontinuation Hospitalization if clinically appropriate Establish causality Complete liver CRF 	Investigator discretion

^aElevated ALT/AST $> 3 \times$ ULN and TBL $> 2 \times$ ULN but without notable increase in ALP to $> 2 \times$ ULN

^b(General) malaise, fatigue, abdominal pain, nausea, or vomiting, or rash with eosinophilia

^cResolution is defined as an outcome of one of the following: (1) return to baseline values, (2) stable values at three subsequent monitoring visits at least 2 weeks apart, (3) remain at elevated level after a maximum of 6 months, (4) liver transplantation, and (5) death.

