Part A: Single-ascending dose study

In Part A sequential cohorts of 8 healthy subjects per cohort will be randomized to receive successively higher single iv doses of KAE609 or matching placebo. In each cohort, subjects will be randomized in a 3:1 ratio to KAE609 (6 subjects/cohort) or matching placebo (2 subjects/cohort). Five planned dose cohorts will be included in Part A (A1, A2, A3, A4 and A5). Provisional dose levels are described in [Section 6.5.1.2](#).

Commercially Confidential Information

For a detailed outline of safety and other assessments, please refer to Part A Assessment Schedule ([Table 8-1](#)). If added, any additional dose cohort will follow the same Part A [Assessment Schedule](#).

Figure 3-2 Study design - SAD

Commercially Confidential Information

Part B: Multiple-ascending dose study

In Part B sequential cohorts of 9 healthy subjects per cohort will be randomized to receive successively higher iv doses of KAE609 or matching placebo. Two planned dose cohorts will be included in Part B (B1 and B2). For Cohort B1, healthy subjects will receive a 60 mg dose of KAE609 or matching placebo iv q24h for 5 days. For Cohort B2, healthy subjects will receive a 120 mg dose of KAE609 or matching placebo iv q24h for 5 days. In each cohort, subjects will be randomized in a 2:1 ratio to KAE609 (6 subjects/cohort) or matching placebo (3 subjects/cohort). Provisional dose levels are described in [Section 6.5.1.2](#)

Commercially Confidential Information

For a detailed outline of safety and other assessments, please refer to Part B Assessment Schedule ([Table 8-2](#)). Any additional cohort will follow the same Part B [Assessment Schedule](#).

Figure 3-3 Study design - MAD

Commercially Confidential Information

4 Rationale

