4.1 Rationale for study design

This is the first clinical study for KAE609 administered iv with the purpose of establishing safety, tolerability and pharmacokinetics in healthy subjects. The rationale for key design elements in this study include:

- **Healthy subjects:** Enrolling healthy subjects was chosen to reduce the risk of introducing confounding variables and to minimize the risk and severity of adverse events. This minimizes any underlying disease-related findings that may confound data interpretation that may exist, especially regarding transaminase elevations, which have been seen in patients with uncomplicated malaria treated with KAE609 and can be present in patients with severe malaria.
- **Randomization:** Helps to avoid possible bias in the selection and allocation of subjects.
- **Placebo comparator:** Use of a placebo helps assess if any safety or tolerability findings should be attributed to KAE609 and helps to maintain study blinding.
- **Blinding:** Blinding of subjects with limited un-blinding of investigators and sponsor minimizes bias in the conduct of the study. The Sponsor's clinical trial team will be blinded. Representatives of the Sponsor, such as the Translational Medicine Expert, may be only unblinded to facilitate safety-related decisions. Limited un-blinding of the investigators and sponsor (e.g., at the time of dose-escalation review) will be allowed if needed to help with safety-related decisions. The pharmacist at the CRO who prepares the injections will be unblinded.
- **Sequential cohorts:** This allows for an adequate safety and tolerability assessment prior to the initiation of each ascending dose.
- **Sentinel dosing:** No sentinel dosing is planned for this study. The predicted toxicities are monitorable and reversible. There is no expected effect on QT and no CNS toxicities expected in this study. A QT potential risk was seen in the hERG assay but no effect of oral KAE609 on QTcF has been observed in healthy subject or patient studies so far. Sentinel dosing is not likely to reduce the risk in this study.
- **Domiciliation:** Subjects will be domiciled before and during dosing and after last dosing to allow for close observation of safety and tolerability, and to ensure compliance with instructions for all subjects.

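### In Part B, the only mandatory stop in Table 16-2 for an isolated, asymptomatic ALT/AST elevation of >5 to ≤8 × ULN cannot act within the five daily doses

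*Protocol*

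**What the plan says.** Protocol Table 16-1 classes ALT or AST above 5 × ULN as a liver event. Section 9.1.1 sends liver events to Appendix 1 for guidance on discontinuation.

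In Table 16-2, the row for >5 to ≤8 × ULN has three steps that bear on dosing. Liver function tests (LFTs) are repeated within 48 hours. Then "If elevation persists, continue follow-up monitoring". Then "If elevation persists for more than 2 weeks, discontinue the study drug". The remaining bullets concern causality and the liver CRF. For isolated total bilirubin (TBL) above 2 × ULN, the table also asks for a repeat within 48 hours but continues: "If elevation persists, discontinue the study drug immediately". Other rows stop treatment at once: ALT or AST above 8 × ULN, above 3 × ULN with INR above 1.5 or with symptoms, potential Hy's Law cases, and jaundice.

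Section 3 sets the Part B regimen. In Cohort B1, "healthy subjects will receive a 60 mg dose of KAE609 or matching placebo iv q24h for 5 days". In Cohort B2, "healthy subjects will receive a 120 mg dose of KAE609 or matching placebo iv q24h for 5 days". Section 12.4.1 places EOS for Part B at Day 12.

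Outside the table, these provisions bear on the same event:

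- **9.1.1:** the investigator has to stop treatment if continuing would harm the subject's well-being. Its list of mandatory reasons includes safety risk and laboratory abnormalities (LFT increase is the example) that the investigator judges to rule out further dosing.
- **10.2.1:** every liver event is repeated. On confirmation, interruption is to be considered, and the drug is discontinued if appropriate.
- **9.1.4:** dosing within a cohort is paused for SAEs not clearly due to other causes, or on the sponsor's view of laboratory findings, with no minimum count.
- **14.1:** the investigator is expected to act at once for a subject's safety, even against the protocol.

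**The concern.** A two-week persistence rule suits a treatment given for weeks or months. Here dosing is over in five days. The row that governs this liver event contains a stop that cannot be met while there is anything left to stop. On the days when a stop could matter, the row itself points only to monitoring. It lacks even the prompt to consider interruption that Table 16-2 gives for adverse events suggestive of liver toxicity, and that Table 16-3 gives for acute kidney injury.

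At stake is whether a healthy subject, for whom Section 4.5 expects no benefit, receives further daily iv doses after a confirmed transaminase elevation above 5 × ULN, and whether two investigators would decide alike. Section 4.1 states: "This is the first clinical study for KAE609 administered iv". It also explains the choice of healthy subjects by the wish to limit disease-related confounding, "especially regarding transaminase elevations, which have been seen in patients with uncomplicated malaria treated with KAE609". The type of event is therefore one the sponsor has in view.

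**Working it through.** The plan states no figure on this point, so there is none to reproduce. The check is arithmetic on dates.

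**Inputs**

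- Stop criterion: more than 14 days of persistence (Table 16-2).
- Doses: Days 1, 2, 3, 4 and 5, i.e. 0, 24, 48, 72 and 96 h (Section 3, q24h for 5 days).
- EOS: Day 12 (Section 12.4.1).
- Active subjects: 2 cohorts × 6 = 12. All blinded Part B subjects, to whom the row applies: 2 × 9 = 18 (Section 3).

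**Step 1: when the rule is met.** Day met = onset day + 14. Delay after last dose = day met − 5. Delay after EOS = day met − 12.

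| Onset | Met only after | Days after last dose | Days after EOS | Doses withheld |
|---|---|---|---|---|
| Day 1 | Day 15 | 10 | 3 | 0 |
| Day 2 | Day 16 | 11 | 4 | 0 |
| Day 3 | Day 17 | 12 | 5 | 0 |
| Day 4 | Day 18 | 13 | 6 | 0 |
| Day 5 | Day 19 | 14 | 7 | 0 |

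Onset at baseline (Day −1, −24 h) gives −24 + 336 = 312 h. That is Day 14, 9 days after the last dose, and again no dose is withheld.

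**Step 2: what onset would let the rule act.** To withhold the fifth dose at 96 h, onset must precede 96 − 336 = −240 h, i.e. more than 10 days before the first dose. That falls in screening, when laboratory tests are part of eligibility (Sections 5.1 and 8.1).

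**Step 3: illustration of what a workable rule could withhold.** The Part B chemistry schedule is not visible, so let *r* be the number of doses left when the elevated result becomes known. Assume that the repeat confirms the elevation and that no judgement-based stop is used. Drug remaining is 60*r* mg in B1 and 120*r* mg in B2. If the repeat is read at the full 48 hours and dosing goes on meanwhile, two doses are given first, so max(0, *r* − 2) are withheld. If doses are held until a repeat taken before the next dose is read, all *r* are withheld.

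| *r* | B1 drug left | B2 drug left | Current row | Stop on 48 h repeat, no hold | Hold, repeat before next dose |
|---|---|---|---|---|---|
| 4 | 240 mg | 480 mg | 0 | 2 | 4 |
| 3 | 180 mg | 360 mg | 0 | 1 | 3 |
| 2 | 120 mg | 240 mg | 0 | 0 | 2 |
| 1 | 60 mg | 120 mg | 0 | 0 | 1 |

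If Part B sampled chemistry at 24 h and 72 h as Table 8-1 does for Part A (an assumption), and results were known before that day's dose, *r* would be 4 or 2. Copying the bilirubin row without a hold would therefore gain nothing when two or fewer doses remain.

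**The case against.** The strongest reply is that the decision exists elsewhere. Section 10.2.1 covers every liver event, has no two-week wait, and brings interruption and discontinuation up for consideration once an elevation is confirmed. It presents Table 16-2 as further detail. Section 9.1.1 obliges the investigator to stop if continuing would harm the subject, and it names LFT increase. Sections 9.1.4 and 14.1 add a sponsor-level pause and immediate safety action. Subjects are domiciled. Redactions fall inside the 9.1.1 list, in 6.5 and after 10.2.2, and any of these could hold a numeric threshold. All of this stands. A reader might infer that the protocol has no way to stop dosing in this band, or that the row tells sites to go on dosing. The documents support neither: the row is silent on dosing, and the other clauses provide for a stop.

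A second reply concerns the bilirubin comparison. Table 16-2 grades its responses, and isolated ALP above 2 × ULN is a liver event with no stop at all. This also stands. The contrast shows that a confirm-then-stop form is already in use in the table. It does not show that the ALT/AST row is a drafting error, and the threshold is a medical choice.

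Third, the likelihood is unknown. Section 4.1 reports elevations in patients, without grade, timing or rate. Section 4.5 describes oral dosing in healthy subjects as safe and well tolerated up to 300 mg single and 150 mg daily for 3 days. No frequency can be attached to this band.

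None of the three makes the two-week stop able to act in Part B.

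**Conclusion.** The point holds in a narrow form. For an isolated, asymptomatic ALT/AST elevation of >5 to ≤8 × ULN while Part B doses remain, the only mandatory stop in Table 16-2 withholds 0 of 5 doses for any onset from Day −1 onward. At the earliest on-treatment onset it is met 10 days after dosing ends. Whether dosing continues after confirmation is then a matter of judgement under Sections 9.1.1, 10.2.1, 9.1.4 and 14.1, unless a redacted passage sets a limit.

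This is a cheap improvement, not a finding that subjects are unprotected. It does not extend to Part A, which is single dose, or to elevations that fall under a row with an immediate stop. The timing result needs only the q24h × 5 regimen and the 14-day criterion. The milligram and doses-withheld figures are illustrative, because they depend on sampling times that the visible text does not give.

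**What to change.** For Part B, replace the follow-up-monitoring bullet and the two-week bullet in the >5 to ≤8 × ULN row with:

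> Repeat LFT before the next scheduled dose; give no further dose until the repeat result is known; if the elevation is confirmed, or the repeat is not available by the next scheduled dose time, discontinue the study drug.

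Keep the causality and liver CRF bullets and the follow-up monitoring column. Cross-refer the row to 10.2.1, 9.1.1 and any redacted stop for this band. The sponsor's medical team should confirm the threshold. Section 9.1.1 needs no change: its clause on deviation from the planned regimen can stand, because under this wording a dose is given on time or not at all.

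The change is two table bullets and a cross-reference, by protocol amendment, with no effect on sample size or analyses. The downside is an occasional early stop on a transient elevation or a late repeat result. Each stopped active subject costs one of six multiple-dose PK profiles in that cohort. Domiciled subjects (4.1) and a local laboratory (8.4.1) should often make the repeat feasible in time.
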